4.2. Discussion of Study Design, Including the Choice of Control Groups

This study uses a dose comparison concurrent control design. All subjects receive the same study product (A/H7N9 IIV) with differing dosages with or without MF59 adjuvant.

4.3. Selection of Study Population

The study population for this clinical trial is 371 males and non-pregnant females, 18-64 years of age, who are in good health and meet all eligibility criteria. The subjects will be recruited from the general population at the participating Vaccine Trial and Evaluation Unit (VTEU) sites that have substantial experience conducting large influenza vaccine studies.

4.4. Treatments

4.4.1. Treatments Administered

A/H7N9 Vaccine and MF59 Adjuvant will be administered.

4.4.2. Identity of Investigational Product

See the study protocol for details of study product formulation.

4.4.3. Method of Assigning Subjects to Treatment Groups (Randomization)

Enrollment/randomization will be performed through the enrollment module in the electronic data capture system maintained by the Statistical and Data Coordinating Center (SDCC).

Eligible subjects will be stratified by clinical site and prior receipt of at least one of the 2017-2018 and/or 2018-2019 seasonal influenza vaccines then randomly assigned with allocation (2:2:2:1) to one of 4 study arms indicated in [Table 1](#). The treatment sequence was generated using permuted block randomization to provide an approximately balanced allocation to the study arms during the study.

4.4.4. Selection of Doses in the Study

Participants in this study are to receive two A/H7N9 vaccinations at HA doses of 3.75, 7.5, or 15 mcg with MF59 adjuvant, or at a HA dose of 15 mcg without adjuvant. The 3.75, 7.5, or 15 mcg with MF59 doses are selected to evaluate safety and immunogenicity of antigen sparing dose strategies. Per FDA Guidance [5], the 15mcg non-adjuvanted dose was selected to compare immune response with the 15 mcg adjuvanted vaccine.

4.4.5. Selection and Timing of Dose for Each Subject

Each subject is to be randomly assigned to a study group which will define the A/H7N9 vaccine dose and receipt of adjuvant for both planned study vaccinations. The first vaccination takes place on the day of randomization, and the second vaccination takes place approximately 21 days after the first vaccination (protocol defined window of 21-28 days post first vaccination).

4.4.6. Blinding

This trial is double-blinded; subjects, investigators, study personnel performing any study-related assessments following study vaccine administration, and laboratory personnel performing antibody assays are blinded to dosage within study vaccination schedule.

The randomization scheme was generated by the SDCC and provided to unblinded study personnel (i.e., pharmacists performing study vaccination preparations and unblinded study vaccine administrators) at the participating VTEU sites who will not be not involved in study-related assessments or have subject contact for data collection following study vaccine administration.

The Data and Safety Monitoring Board (DSMB) may receive data in aggregate and presented by group. The DSMB may also be provided with expected and observed rates of the expected AEs in an unblinded fashion, and may request treatment assignment be unblinded for an individual subject if required for safety assessment. The DSMB will review grouped and unblinded data in the closed session only.

4.4.7. Prior and Concomitant Therapy

Administration of any medications, therapies, or vaccines (including prescription and over-the-counter drugs as well as herbals, vitamins, and supplements) from 60 days prior to study vaccination through 180 days post final vaccination will be solicited from the participant during screening, enrollment, and follow-up. Any reported prior therapies from up to 30 days prior to vaccination through 180 days post final vaccination will be recorded in the appropriate data collection form.

Prior receipt of a licensed seasonal influenza vaccine over the current (2018-2019) and previous two seasons (2016-2017 and 2017-2018) is not exclusionary as long as it has been administered within the allowable window (protocol Section 5.1.2).

Use of concomitant medications is allowed prior to and during the trial with the exception of medications and therapies that might interfere with the evaluation of the investigational product. Medications in this category include the prohibited medication per the Subject Exclusion Criteria (protocol Section 5.1.2). In addition, the site principal investigator or appropriate sub-investigator may identify other medications that should not be used due to a risk to subject safety or assessment of reactogenicity and immunogenicity.

4.4.8. Treatment Compliance

All subjects are to receive two doses of study product administered in the clinic.

4.5. Immunogenicity and Safety Variables

See [Table 2](#) and [Table 3](#) for schedule of study procedures.

4.5.1. Safety Variables

Safety will be assessed by the frequency and severity of:

1. SAEs occurring from the time of the first study vaccination through approximately 12 months after the last study vaccination.
2. Solicited AEs – reactogenicity events occurring from the time of each study vaccination through 7 days after each study vaccination:
 - a) Injection site reactions including pruritus, ecchymosis, erythema, induration/swelling, pain, and tenderness.
 - b) Systemic reactions including fever, feverishness, fatigue, malaise, myalgia, arthralgia, headache, and nausea.
3. Clinical safety laboratory AEs occurring from the time of each study vaccination through approximately 7 days after each study vaccination. Parameters to be evaluated include white blood cells (WBC), hemoglobin (Hgb), platelets (PLT), alanine aminotransferase (ALT), total bilirubin (T. Bili), and creatinine (Cr).
4. Unsolicited AEs – non-serious AEs occurring from the time of each study vaccination through approximately 21 days after each study vaccination.
5. MAAEs, including NOCMCs, and PIMMCs occurring from the time of the first study vaccination through approximately 12 months after the last study vaccination.

Grading scales for injection site and systemic solicited reactions, vital signs, and clinical laboratory parameters are provided in [Table 9](#), [Table 10](#), [Table 11](#), and [Table 12](#).

4.5.2. Immunogenicity Variables

Individual HAI and Neut results will be reported by the central immunology laboratory for the homologous vaccine strain, A/Hong Kong/125/2017 (H7N9), and heterologous strains, A/Shanghai/2/2013 (H7N9) and A/Guangdong/17SF003/2016xPR8/17SF003/2016xPR8 (H7N9). Assay results are reported as a reciprocal titer with values of $10 \cdot 2^k$, where $k=0, 1, 2$, etc. The lower limit of detection for the HAI and Neut assays is 1:10; values below the limit of detection are imputed for analysis as one-half the limit of detection ($10/2 = 5$). For analysis, the geometric mean (calculated on natural log scale) of repeated results for each sample will be computed and used as the response for all subsequent calculations. The variation arising from multiple measurements for an individual at a single time point is not used in subsequent calculations. See Section 3.3 for definitions of derived variables for the analysis of HAI and Neut data.

To assess the Neuraminidase Antigen (NA) specific antibody response to vaccination, it is first necessary to determine the NA content of inactivated influenza vaccine; this assay is under development. If successful, the NA content in a dosage specific manner can be correlated to the N9 NA-specific antibody responses elicited by the 2017 H7N9 IIV. An addendum to the SAP will be generated to outline the planned analyses when assay development is complete.

All immunogenicity data will be uploaded into the SDCC's electronic data capture system.

5. SAMPLE SIZE CONSIDERATIONS

This study is planned to enroll 106 subjects in each adjuvanted study arm and 53 subjects in the unadjuvanted study arm. Randomization at each site will be stratified by prior receipt of season influenza vaccines, however there is no enrollment target for these strata. The sample size for this study was selected to obtain preliminary estimates in a time critical manner. While this study is not designed to test any specific null hypothesis, the following tables illustrate the precision and power that is available for select estimates and comparisons of interest.

[Table 4](#) indicates the probability of observing one or more safety events, such as solicited injection site or systemic reactogenicity events or an unsolicited non-serious AE of a particular type for a single study arm (N = 53, 106) and for all subjects receiving adjuvanted vaccine (N = 318).

Binomial confidence intervals (CI) are widest (have the least precision) when the response rate is 50%. [Table 5](#) is presented to indicate the worst-case scenario for precision of observed exact (Clopper-Pearson) binomial confidence intervals.

[Table 6](#) illustrates the minimum detectable differences in the proportion of subjects responding (e.g., attaining seroconversion or a titer $\geq 1:40$) between two adjuvanted study arms within each stratum using a two-sided Likelihood Ratio Test and $\alpha = 0.05$.

Power calculations assume $n=100$ per adjuvanted group and $n=50$ for the unadjuvanted group. Based on previous DMID A/H7N9 trials it is expected 5% of enrolled subjects in this stratum may be excluded from analysis of the primary endpoint. In the event that only 100 subjects are actually enrolled in a study arm, the small dropout rates anticipated would have a minimal impact on the calculations presented in [Table 7](#).

Per FDA guidance [5,6], for differences in HAI antibody response rates, the lower confidence limit on the appropriate point estimate excluding equality (i.e., 0 for the difference parameter) may be sufficient to demonstrate the added value of the adjuvant. [Table 7](#) shows the lower bound of the 95% confidence interval for the difference in the proportion of responders between the adjuvanted and unadjuvanted arms (e.g. 15 mcg + MF59 minus 15 mcg unadjuvanted) assuming the proportion of responders in the unadjuvanted arm is 0.10 and considering a range for the proportion of responders in the adjuvanted arm ranges from 0.50 to 0.90.

6. GENERAL STATISTICAL CONSIDERATIONS

6.1. General Principles

All continuous variables will be summarized using the following descriptive statistics: n (non-missing sample size), mean, standard deviation, median, maximum and minimum. The frequency and percentages (based on the non-missing sample size) of observed levels will be reported for all categorical measures. In general, all data will be listed, sorted by site, study arm and subject, and when appropriate by visit number within subject. All summary tables will be structured with a column for each study arm in the following order:

- Arm 1: 3.75 mcg A/H7N9 + MF59
- Arm 2: 7.5 mcg A/H7N9 + MF59
- Arm 3: 15 mcg A/H7N9 + MF59
- Arm 4: 15 mcg A/H7N9

All tables will be annotated with the total population size relevant to that table/arm, including any missing observations.

6.2. Timing of Analyses

6.2.1. CSR

Once the last subject completes the visit that occurs approximately at Day 387, the clinical database will be cleaned, monitored, and locked. The CSR will be completed when all safety data through Day 387 and all humoral immunogenicity data through Day 202 are completed and uploaded.

Upon receipt of humoral immunogenicity against homologous influenza A/Hong Kong/125/2017 (H7N9) virus through Day 202 and non-clinical data lock, a subset of predefined “topline tables” will be generated by the SDCC concurrently with CSR generation. These tables will include summaries of safety and immunogenicity data and will represent the final analyses of primary endpoints; as such no p-value adjustment is required. These analyses may be made available to the sponsor for planning subsequent trials and to the lead PI for publication. Tables to be included in the topline set are indicated with the symbol * in the title.

Analysis of exploratory immunogenicity endpoints may be performed and released as the data are available from the research laboratory. Any such analyses would be considered the final analysis for the endpoint and included in the CSR. Additional exploratory immunogenicity endpoint data not available at the time of CSR preparation may be included in an addendum to the CSR.

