3.2. Endpoints

3.2.1. Primary

Safety:

- Occurrence of study vaccine-related serious adverse events (SAEs) from the time of the first study vaccination through approximately 12 months after the last study vaccination.
- Occurrence of solicited injection site and systemic reactogenicity events from the time of each study vaccination through 7 days after each study vaccination.
- Occurrence of clinical safety laboratory adverse events from the time of each study vaccination through approximately 7 days after each study vaccination.

Immunogenicity:

- For HAI and Neut antibodies, percentage of subjects achieving seroconversion against the influenza 2017 H7N9 study vaccine strain (defined as either a pre-vaccination titer <1:10 and a post-vaccination titer \geq 1:40 or a pre-vaccination titer \geq 1:10 and a minimum four-fold rise in post-vaccination titer) at approximately 21 days after the second study vaccination (Study Day 43).
- For HAI and Neut antibodies, percentage of subjects achieving titer \geq 1:40 against the influenza 2017 H7N9 study vaccine strain at approximately 21 days after the second study vaccination (Study Day 43).
- Geometric Mean Titers (GMTs) of serum HAI and Neut antibodies against the influenza 2017 H7N9 vaccine strain at approximately 21 days after the second study vaccination (Study Day 43).

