6.6. Interim Analyses and Data Monitoring

Interim analyses will only be used to terminate this trial in the event that unanticipated safety events deemed to be of sufficient concern require such action by the sponsor. These assessments will not be made on the basis of testing a formal statistical hypothesis; therefore, p-value adjustment will not be made to any analyses. A DSMB will be convened by DMID to review study progress and participant, clinical, safety, and reactogenicity and immunogenicity data.

Clinical, safety, and reactogenicity data through approximately 180 days after the second study vaccination will represent the primary clinical database for this trial. Once the last subject completes the visit that occurs approximately 180 days after second study vaccination and all HAI and Neut results are received, a “topline” subset of the immunogenicity and safety tables will be provided to DMID on an expedited timeline. These analyses may be made available to the sponsor for planning subsequent trials and to the lead PI for publication and will be considered the final analysis of these data.

Emergent public health needs may dictate additional interim safety, reactogenicity, and/or immunogenicity analyses be performed on available information at any time during the trial. If this occurs, immunogenicity data will be analyzed as results are available from the central immunogenicity laboratory.

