14.3 Safety Data

14.3.1 Displays of Adverse Events

Table 63: Overall Summary of Adverse Events – Safety Population*

	Study Arm 1 3.75 mcg A/H7N9 + MF59 (N=X)		Study Arm 2 7.5 mcg A/H7N9 + MF59 (N=X)		Study Arm 3 15 mcg A/H7N9 + MF59 (N=X)		Study Arm 4 15 mcg A/H7N9 (N=X)		All Subjects (N=X)	
	n	%	n	%	n	%	n	%	n	%
Subjects ^a with										
At least one injection site solicited adverse event	X	X	X	X	X	X	X	X	X	X
At least one systemic solicited adverse event	X	X	X	X	X	X	X	X	X	X
At least one unsolicited adverse event	X	X	X	X	X	X	X	X	X	X
At least one related unsolicited adverse event	X	X	X	X	X	X	X	X	X	X
Mild (Grade 1)	X	X	X	X	X	X	X	X	X	X
Moderate (Grade 2)	X	X	X	X	X	X	X	X	X	X
Severe (Grade 3)	X	X	X	X	X	X	X	X	X	X
At least one severe (Grade 3) unsolicited adverse event	X	X	X	X	X	X	X	X	X	X
Related	X	X	X	X	X	X	X	X	X	X
Unrelated	X	X	X	X	X	X	X	X	X	X
At least one serious adverse event ^b	X	X	X	X	X	X	X	X	X	X
At least one related, serious adverse event	X	X	X	X	X	X	X	X	X	X
At least one adverse event leading to early termination ^c	X	X	X	X	X	X	X	X	X	X
At least one medically attended adverse event	X	X	X	X	X	X	X	X	X	X

Table 63: Overall Summary of Adverse Events *(continued)*

	Study Arm 1 3.75 mcg A/H7N9 + MF59 (N=X)		Study Arm 2 7.5 mcg A/H7N9 + MF59 (N=X)		Study Arm 3 15 mcg A/H7N9 + MF59 (N=X)		Study Arm 4 15 mcg A/H7N9 (N=X)		All Subjects (N=X)	
	n	%	n	%	n	%	n	%	n	%
Subjects ^a with										
At least one new onset chronic medical condition	x	x	x	x	x	x	x	x	x	x
At least one potentially immune mediated medical condition	x	x	x	x	x	x	x	x	x	x
Note: N = Number of subjects in the Safety population. ^a Subjects are counted once for each category regardless of the number of events. ^b A listing of Serious Adverse Events is included in Section 14.3.2. ^c As reported on the Adverse Event eCRF.										

Table 64: Number of Adverse Events Occurring in 5% of Subjects in Any Study Arm by MedDRA® System Organ Class and Preferred Term, and Treatment Group - Safety Population

[Implementation note: This table includes solicited events, unsolicited events, and clinical laboratory events. Sort by SOC then PT]

Preferred Term	MedDRA System Organ Class	Study Arm 1 3.75 mcg A/H7N9 + MF59 (N=X)			Study Arm 2 7.5 mcg A/H7N9 + MF59 (N=X)			Study Arm 3 15 mcg A/H7N9 + MF59 (N=X)			Study Arm 4 15 mcg A/H7N9 (N=X)			All Subjects (N=X)		
		n	%	Events	n	%	Events	n	%	Events	n	%	Events	n	%	Events
Serious Adverse Events																
All	All	x	x	x	x	x	x	x	x	x	x	x	x	x	x	x

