14.2.2 Immunogenicity Figures

Figure 2: Reverse Cumulative Distribution of Hemagglutination Inhibition Antibody against A/Hong Kong/125/2017 (H7N9) by Study Day, and Study Arm - Modified Intent to Treat Population

[Implementation Note: A generic sample figure is shown below. The RCD curves should be presented in a single figure with separate panels for each study day (Baseline, Day 8, Day 22, Day 29, Day 43, Day 202). Figures generated for preliminary report will include data from all available visits at the time of report generation. Visit labels should be included in the panel headers. Within each panel individual curves should be used for each study arm (four curves).]

Figures with similar format:

Figure 3: Reverse Cumulative Distribution of Hemagglutination Inhibition Antibody against A/Hong Kong/125/2017 (H7N9) by Study Day, and Study Arm - Per-Protocol Population

[figure not shown]
Figure 4: Reverse Cumulative Distribution of Neutralizing Antibody Against A/Hong Kong/125/2017 (H7N9) by Study Day, and Study Arm - Modified Intent-to-Treat Population

Figure 5: Reverse Cumulative Distribution of Neutralizing Antibody against A/Hong Kong/125/2017 (H7N9) by Study Day, and Study Arm - Per-Protocol Population

Figure 6: Geometric Mean Titers of Hemagglutination Inhibition Antibody Against A/Hong Kong/125/2017 (H7N9) by Study Day, and Study Arm - Modified Intent-to-Treat Population

[Implementation Note: A generic sample figure is shown below. Planned Study Day is plotted along the x-axis, with visit labels as tick labels. Titer is plotted on the y-axis on the log-10 scale. GMT should be plotted at each visit with upper and lower error bars for the 95% CI for each treatment group with different marker shapes/colors for each study arm. Each study arm should have a separate color and marker shape.]

Note: this figure will be generated for the preliminary report including data through Day 43, then re-generated for the final CSR to include all data through Day 202.

Figures with similar format:

Figure 7: Geometric Mean Titers of Hemagglutination Inhibition Antibody against A/Hong Kong/125/2017 (H7N9) by Study Day and Study Arm - Per-Protocol Population

Figure 8: Geometric Mean Titers of Neutralizing Antibody against A/Hong Kong/125/2017 (H7N9) Study Day and Study Arm - Modified Intent-to-Treat Population

Figure 9: Geometric Mean Titers of Neutralizing Antibody against A/Hong Kong/125/2017 (H7N9) by Study Day and Study Arm - Per-Protocol Population

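### The SAP gives the topline tables two release times, and at the earlier one they would report the 12-month vaccine-related SAE endpoint before any subject has completed it

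*SAP*

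**What the plan says.** **The endpoint.** SAP 3.2.1, like protocol 3.3.1, lists vaccine-related SAEs as a primary safety endpoint, followed "from the time of the first study vaccination through approximately 12 months after the last study vaccination". The other primary endpoints close much earlier: solicited events and laboratory AEs about 7 days after each dose, immunogenicity at Day 43.

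**Timing in SAP 6.2.1.** The clinical database is locked after the last Day 387 visit, and the CSR needs safety data to that day. The topline tables follow receipt of homologous-strain titers through Day 202 and a non-clinical data lock. They "will be generated by the SDCC concurrently with CSR generation" and "will represent the final analyses of primary endpoints".

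**Timing in SAP 6.6.** The release condition is different: "Once the last subject completes the visit that occurs approximately 180 days after second study vaccination and all HAI and Neut results are received". SAP 6.6.2 repeats it. Both describe an expedited release, possible use in publication and in planning later trials, and final status for the data included. Protocol 10.5 has the same trigger. Protocol 10.4 and 10.5 both expect subjects to be in long-term safety follow-up at release.

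**The table.** An asterisk marks the topline set. Table 63 carries one, and among its rows is "At least one related, serious adverse event". It also has rows for all SAEs, MAAEs, NOCMCs and PIMMCs, which are collected over the same 12 months. Its shell has no data-cut footnote.

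**The concern.** The two release times give Table 63 different standing. If topline comes with the CSR, after Day 387, the related-SAE row is complete and may be called final. If it comes after the last Day 202 visit, that row is an interim count of a primary endpoint, and nothing in the table says so.

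A by-arm related-SAE count could then be published as final and later differ from the CSR. This matters more than usual because protocol 2.3.1 states that the vaccine has not been evaluated in humans before. The same applies to the MAAE, NOCMC and PIMMC rows, which are secondary endpoints.

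**Working it through.** **Inputs**
- Dose 2 is on Day 22. Visit 10 is Day 181 and Visit 11 is Day 366 after dose 2, each ±14 days; the dose 2 window is +7 days (protocol 6.4.1, 6.4.2 and Appendix A).
- Enrolment takes about 12 weeks, or 84 days (protocol section 5). As a sensitivity value, the protocol summary's 17 months in total less 13 months per subject gives 4 months, about 122 days.
- N = 371.
- The delay T from the last Day 202 visit to the data cut (assays and lock) is not stated. It is assumed to lie between 0 and 185 days.
- Accrual is assumed uniform, with visits on schedule unless noted.

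**Step 1: reproduce the visit days.** The day of dose 2 counts as Day 1, so Visit 10 = 22 + 181 − 1 = Day 202 and Visit 11 = 22 + 366 − 1 = Day 387. Both match the documents. The gap is 387 − 202 = 185 days.

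**Step 2: follow-up outstanding at T = 0.** Day 1 to Day 387 is 386 days.
- Last subject enrolled: 185/386 = 47.9%.
- First subject enrolled, 84-day accrual: at Day 202 + 84 = 286, so (387 − 286)/386 = 101/386 = 26.2%.
- First subject enrolled, 122-day accrual: at Day 202 + 122 = 324, so 63/386 = 16.3%.

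No subject has reached Day 387 under either accrual period.

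**Step 3: window extremes.** Put the last subject's dose 2 at +7 and Visit 10 at +14, so that Visit 10 falls on Day 223. The first subject is then at Day 307 (84-day accrual) or Day 345 (122-day accrual). The earliest permitted Visit 11 is 387 − 14 = Day 373. The number complete is still 0 of 371.

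**Step 4: effect of delay.** With enrolment period E, the share complete is (202 + E + T − 387)/E, held between 0 and 1.

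| T (days) | Complete of 371, E = 84 | Complete of 371, E = 122 |
|---|---|---|
| 0 | 0 | 0 |
| 60 | 0 | 0 |
| 90 | 0 | 82 |
| 120 | 84 | 173 |
| 150 | 216 | 265 |
| 185 | 371 | 371 |

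For example, at T = 120 and E = 84 the share is (202 + 84 + 120 − 387)/84 = 19/84 = 0.226, and 0.226 × 371 = 84.

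**Step 5: endpoints complete at Day 202.** Day 43 immunogenicity and the 7-day solicited and laboratory endpoints are complete. Of the primary endpoints, only vaccine-related SAEs are not.

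**The case against.** The strongest defence is that SAP 6.2.1 is correct on its own terms. It opens with lock after Day 387, ties topline to the CSR, and mentions Day 202 only to describe the titers. The places with a clear Day 202-visit trigger claim finality only for the data included, not for primary endpoints. So no single sentence declares a Day 202 SAE count to be the final analysis of the 12-month endpoint. That is true, but it saves SAP 6.2.1 only by setting it against SAP 6.6, SAP 6.6.2 and protocol 10.5. SAP section 12 says there are no changes from the protocol's analyses, so it cannot be taken as a deliberate override.

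It is also fair that complete SAE reporting is assigned to the CSR. Tables 84 to 86, which list SAEs, PIMMCs and NOCMCs, are not starred, and the CSR waits for Day 387. Table 63 is an overview.

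A reader might infer more in two places, and the documents do not support either inference.

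- *A third, incompatible topline date.* The note to Figure 6 says "this figure will be generated for the preliminary report including data through Day 43". That figure has no asterisk, so it is outside the topline set. A Day 43 preliminary report can coexist with a later topline release and the CSR. What remains is that the report is not defined in the SAP's section on timing of analyses.
- *Unblinded judgement of relatedness after topline.* Protocol 10.5 anticipates this: blinded investigators and medical monitors who take no part in analysis or reporting go on assessing SAEs, MAAEs, PIMMCs and new-onset chronic conditions until the last follow-up visit. It also bars use of topline for decisions on trial conduct.

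**Conclusion.** The conflict is real and limited to timing and labelling. Following SAP 6.6 and protocol 10.5 while applying the SAP 6.2.1 label would release an incomplete related-SAE count as final.

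The 26% to 48% outstanding per subject rests on 84-day enrolment and no delay after the last Day 202 visit. It should not be read as the share that will be missing. Slower accrual lowers the bottom of the range, to 16% with 122 days, and a longer delay lowers both ends. Nothing is outstanding at about 185 days. The documents give no basis for estimating how many events would be missed.

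No hypothesis test, significance level or sample size is affected, and the CSR will hold the complete SAE data. The correction should still be made before any topline release, because those tables may be published.

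**What to change.** 1. State one topline trigger in SAP 6.2.1, 6.6 and 6.6.2, consistent with protocol 10.5.
2. If the trigger is the last Day 202 visit, limit the word final in SAP 6.2.1 to endpoints complete at that cut: immunogenicity, solicited events and laboratory AEs.
3. In that case, footnote the SAE, related-SAE, MAAE, NOCMC and PIMMC rows of Table 63: *through data cut, not final; final analysis in the CSR after Day 387*. State the cut date.
4. Separately, define the Day 43 preliminary report in SAP 6.2 or delete it from the Figure 6 note.

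The cost is wording in three SAP sections, one table footnote and one figure note. No data collection or analysis is added.
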